Appendix D. NCCN Risk Categorization: Guidelines for AML Version 2.2014

Risk Category	Cytogenetic
Better Risk	inv(16) or t(16;16) t(8;21) t(15;17)
Intermediate Risk	Normal cytogenetics +8 alone t(9;11) Other non-defined
Poor Risk	Complex(> clonal chromosomal abnormalities) Monosomal karyotype -5,5q-, -7,7q- 11q23-non t(9;11) inv(3),t(3;3) t(6;9) t(9;22)

Appendix E. Recommendations for Initial Management of Electrolyte Imbalances and Prevention of Tumor Lysis Syndrome (TLS)

Abnormality	Management Recommendations
Hyperkalemia (including rapidly rising potassium)	
Potassium ≥ 0.5 mmol/L increase from prior value (even if potassium within normal limits [WNL])	
 Recheck potassium, phosphorus, uric acid, calcium and creatinine in 1 hour STAT. If further ≥ 0.2 mmol/L increase in potassium, but still $<$ upper limit of normal (ULN), manage as per potassium \geq ULN. Otherwise recheck in 1 hour. Resume per protocol testing if change in potassium is < 0.2 mmol/L, and potassium $<$ ULN, and no other evidence of tumor lysis. At discretion of investigator, may recheck prior to hospitalization. If stable or decreased, and still within normal limits (WNL), hospitalization is at the discretion of the investigator. Potassium, phosphorus, uric acid, calcium and creatinine must be rechecked within 24 hours.
Potassium $>$ upper limit of normal	
 Perform STAT ECG and commence telemetry Nephrology (or other acute dialysis service) notification with consideration of initiating dialysis. Administer Kayexalate 60 g (or Resonium A 60 g). Administer furosemide 20 mg IV \times 1. Administer calcium gluconate 100 – 200 mg/kg IV slowly if there is ECG/telemetry evidence of life-threatening arrhythmias. Recheck potassium, phosphorus, uric acid, calcium and creatinine in 1 hour STAT. If potassium $<$ ULN 1 hour later, repeat potassium, phosphorus, uric acid, calcium and creatinine 1, 2 and 4 hours, if no other evidence of tumor lysis.
Potassium ≥ 6.0 mmol/L (6.0 mEq/L) and/or symptomatic (e.g., muscle cramps, weakness, paresthesias, nausea, vomiting, diarrhea)	
 Perform STAT ECG and commence telemetry. Nephrology (or other acute dialysis service) assessment with consideration of initiating dialysis. Administer Kayexalate 60 g (or Resonium A 60 g). Administer furosemide 20 mg IV \times 1. Administer insulin 0.1 U/kg IV + D25 2 mL/kg IV. Administer sodium bicarbonate 1 – 2 mEq/kg IV push. 
 If sodium bicarbonate is used, rasburicase should not be used as this may exacerbate calcium phosphate precipitation. Administer calcium gluconate 100 – 200 mg/kg IV slowly if there is ECG/telemetry evidence of life-threatening arrhythmias. Do not administer in same IV line as sodium bicarbonate. Recheck potassium, phosphorus, uric acid, calcium and creatinine every hour STAT.

Abnormality	Management Recommendations
Hyperuricemia	
Uric acid \geq 8.0 mg/dL (476 μ mol/L)	
 • Consider rasburicase (dose per institutional guidelines). 
 ○ If rasburicase is used, sodium bicarbonate should not be used as this may exacerbate calcium phosphate precipitation. • Recheck potassium, phosphorus, uric acid, calcium and creatinine in 1 hour STAT.
Uric acid \geq 10 mg/dL (595 μ mol/L) OR Uric acid \geq 8.0 mg/dL (476 μ mol/L) with 25% increase and creatinine increase \geq 0.3 mg/dL (\geq 0.027 mmol/L) from pre-dose level	
 • Administer rasburicase (dose per institutional guidelines). 
 ○ If rasburicase is used, sodium bicarbonate should not be used as this may exacerbate calcium phosphate precipitation. • Notify nephrology (or other acute dialysis service). • Recheck potassium, phosphorus, uric acid, calcium and creatinine in 1 hour STAT. • If uric acid $<$ 8.0 mg/dL 1 hour later, repeat potassium, phosphorus, uric acid, calcium and creatinine 2 and 4 hours later, if no other evidence of tumor lysis.
Hypocalcemia	
Calcium \leq 7.0 mg/dL (1.75 mmol/L) AND Patient symptomatic (e.g., muscle cramps, hypotension, tetany, cardiac arrhythmias)	
 • Administer calcium gluconate 50 – 100 mg/kg IV slowly with ECG monitoring. • Telemetry. • Recheck potassium, phosphorus, uric acid, calcium and creatinine in 1 hour STAT. • If calcium normalized 1 hour later, repeat potassium, phosphorus, uric acid, calcium and creatinine 2 and 4 hours later, if no other evidence of tumor lysis.
Hyperphosphatemia	
Phosphorus \geq 5.0 mg/dL (1.615 mmol/L) with \geq 0.5 mg/dL (0.16 mmol/L) increase	
 • Administer a phosphate binder (e.g., aluminum hydroxide, calcium carbonate, sevelamer hydroxide, or lanthanum carbonate). • Nephrology (or other acute dialysis service) notification (dialysis required for phosphorus \geq 10 mg/dL). • Recheck potassium, phosphorus, uric acid, calcium and creatinine in 1 hour STAT. • If phosphorus $<$ 5.0 mg/dL 1 hour later, repeat potassium, phosphorus, uric acid, calcium and creatinine 2 and 4 hours later, if no other evidence of tumor lysis.
Creatinine	
Increase \geq 25% from baseline	
 • Start or increase rate of IV fluids. • Recheck potassium, phosphorus, uric acid, calcium and creatinine in 1 – 2 hours STAT.

Appendix F. Adverse Events Commonly Associated with Acute Myelogenous Leukemia Study Population and/or Progression of Acute Myelogenous leukemia

Fever

Fatigue

Dyspnea

Pain, all types

Thrombocytopenia

Anemia

Neutropenia

Infection (bacterial, viral, fungal)

Neutropenic infection

Neutropenic sepsis

Oral candidiasis

Stomatitis

Periodontal infection

Tooth infection, abscess

Upper respiratory tract infection

Sinusitis, Rhinitis

Bronchitis (bacterial, viral)

Bronchitis chronic

Pneumonia (bacterial, viral, fungal)

Catheter site cellulitis

Herpes zoster disseminated, multi-dermatomal

Herpes zoster

Herpes simplex (oral, genital)

Skin candida

Urinary tract infection bacterial, fungal

Genitourinary tract infection (viral, bacterial, fungal)

Gastroenteritis

Enterocolitis

Malignant disease progression, including death

Hyperleukocytosis, including the symptomatic form (leukostasis)

Leukaemic infiltration brain

Malignant pleural effusion

Chloroma/granulocytic sarcoma

Second primary cancers, all types

Bleeding

Gingival bleeding

Mouth haemorrhage

Epistaxis

Haematuria

Injection site haemorrhage

Petechiae

Skin haemorrhage

Retinal hemorrhage

Population-Related Comorbidities

Hypertension

Rheumatoid arthritis/osteoarthritis

Hyperlipidemia

Peptic ulcer

Inflammatory bowel disease

Coronary artery disease

Peripheral vascular disease

Cardiomyopathy

Valvular disease

Atrial fibrillation

Diabetes mellitus

Chronic obstructive pulmonary disease

Cerebrovascular accident

Transient ischemia attack

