6.1.8.2 Prophylaxis and Management of Tumor Lysis Syndrome (TLS)

There is a potential for TLS for patients with AML receiving induction therapy, especially for those with elevated pretreatment LDH levels, elevated leukocyte count, renal dysfunction, and dehydration. To mitigate the risk for TLS,³⁶ subjects will receive tumor lysis prophylaxis, including hydration (e.g., oral, intravenous) and treatment with an agent to reduce the uric acid level (e.g., allopurinol, rasburicase).^{36,41}

TLS prophylaxis must be initiated in all such subjects prior to the first venetoclax dose or first new escalated dose.

Tumor Lysis Syndrome Prophylaxis and Management for Subjects Dose Escalated in Protocol Version 1 and Amendment 1

- Hospitalization recommended on Day –1 and mandated by Day 1 and for a minimum of 24 hours after any venetoclax dose escalation.
- Nephrology (or other acute dialysis service) should be available on each admission per institutional standards to ensure emergency dialysis is available.
- An agent to reduce the uric acid level (e.g., allopurinol) to be initiated at least 24 hours prior to venetoclax dosing. Treatment may need to be continued for up to 28 days based on the ongoing risk of TLS development. Subjects allergic to allopurinol must use another uric acid reducer starting at least 24 hours prior to venetoclax dosing or rasburicase on the day of treatment (prior to venetoclax dosing).
- Oral hydration (at least 1 to 2 liters) starting from at least 24 hours prior to first venetoclax dose or any dose escalation.
- Intravenous hydration (target 150 to 200 mL/hr, as tolerable) must be started upon admission and continued during hospitalization as appropriate. Urine output must be monitored.

- Chemistries on the first day of venetoclax dosing at 0 (within 4 hours prior to dosing), 4, 8 and 12 hours and each day of a new dose at 0 (within 4 hours prior to dosing), 4, 8 and 12 hours.*
- Chemistries at 24, 48, 72 hours after receiving the first designated target dose.*
- Collection of samples for venetoclax PK assay 8 hours after dosing on each day of new dose. The 8-hour post-dose PK sample may be collected up to 1 hour earlier or up to 20 minutes after the scheduled time, if necessary to facilitate sample processing.

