Appendix H. Tumor Lysis Syndrome Classification

Metabolic Abnormality	Criteria for Classification of Laboratory Tumor Lysis Syndrome*	Criteria for Classification of Clinical Tumor Lysis Syndrome**
Hyperuricemia	Uric acid > 8 mg/dl (475.8 µmol/liter)	N/A
Hyperphosphatemia	Phosphorus > 4.5 mg/dl (1.5 mmol/liter)	N/A
Hyperkalemia	Potassium > 6 mmol/liter	Cardiac dysrhythmia or sudden death probably or definitely caused by hyperkalemia
Hypocalcemia	Corrected calcium < 7.0 mg/dl (1.75 mmol/liter) or ionized calcium < 1.12 mg/dl (0.3 mmol/liter) [#]	Cardiac dysrhythmia, sudden death, seizure, neuromuscular irritability (tetany, paresthesias, muscle twitching, carpopedal spasm, Trousseau's sign, Chvostek's sign, laryngospasm, or bronchospasm), hypotension, or heart failure probably or definitely caused by hypocalcemia
Acute Kidney Injury [!]	N/A	Increase in the serum creatinine level of 0.3 mg/dl (26.5 µmol/liter) or the presence of oliguria (average urine output of < 0.5 ml/kg/hr over a 6-hour period)

* Laboratory TLS requires two or more metabolic abnormalities must be present during the same 24-hour period within 3 days before the start of therapy or up to 7 days afterward.

** Clinical TLS requires the presence of Laboratory TLS plus one or more findings from the Clinical TLS column.

Corrected calcium = measured calcium level in mg/dl + 0.8 × (4 – albumin in gm/dl).

! Acute kidney injury, unless attributable to another cause, represents clinical TLS even if criteria for laboratory TLS are not satisfied.

Cross reference: Howard SC 2011⁴³

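### Appendix E gives two unconditional instructions, sodium bicarbonate in the top potassium row and rasburicase in the higher uric acid row, that exclude each other, with no rule for when both rows apply

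*Protocol*

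**What the plan says.** The passages are in the protocol, in Appendix E (management of electrolyte imbalances), Section 6.1.8.2 (TLS prophylaxis and management) and Appendix H (TLS classification).

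- **Appendix E, top potassium row.** The trigger is "Potassium ≥ 6.0 mmol/L (6.0 mEq/L) and/or symptomatic". One step is "Administer sodium bicarbonate 1 – 2 mEq/kg IV push", followed by the caveat "If sodium bicarbonate is used, rasburicase should not be used as this may exacerbate calcium phosphate precipitation".
- **Appendix E, higher uric acid row.** The trigger is uric acid of at least 10 mg/dL, or at least 8.0 mg/dL with a 25% increase and a creatinine rise of at least 0.3 mg/dL from the pre-dose level. The first step is "Administer rasburicase (dose per institutional guidelines", followed by the caveat "If rasburicase is used, sodium bicarbonate should not be used as this may exacerbate calcium phosphate precipitation".
- **Appendix E, lower uric acid row** (at least 8.0 mg/dL). It carries the same caveat, but the step is only "Consider rasburicase (dose per institutional guidelines".
- **Section 6.1.8.2.** Rasburicase is named in general terms as an example of a prophylactic agent. Under the heading for subjects dose-escalated in Version 1 and Amendment 1, allopurinol-allergic subjects may have another uric acid reducer "or rasburicase on the day of treatment (prior to venetoclax dosing". For Cohort C the agent is left to regional standards or institutional guidelines.
- **Appendix H.** "Laboratory TLS requires two or more metabolic abnormalities must be present during the same 24-hour period". Potassium and uric acid are two of the four laboratory abnormalities listed.

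**The concern.** Each of the two rows gives an instruction without a condition and then excludes the drug that the other row instructs. High potassium and high uric acid are features of the same syndrome, and laboratory TLS is defined by abnormalities occurring together, so the protocol foresees that a subject may meet more than one row.

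This is guidance for urgent use on an adverse event of special interest. Sections 5.1, 5.3.1.1 and 6.1.8.2 all send sites to Appendix E. If both rows apply, a site must depart from one of them, and different sites may depart from different ones. The table's own reason for the caveats is that using the two drugs together may worsen calcium phosphate precipitation, so the ambiguity bears on subject safety.

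**Working it through.** There is no figure to reproduce; this is a check of whether the rules can be followed together.

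**Step 1. Count the rows.** Appendix E has three potassium rows, two uric acid rows, and one each for calcium, phosphorus and creatinine: 3 + 2 + 1 + 1 + 1 = 8. Two of these (top potassium, higher uric acid) carry the conflicting instructions. Three (those two and the lower uric acid row) carry a caveat.

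**Step 2. Test the rules when both rows apply.** There are four statements: give bicarbonate; if bicarbonate, no rasburicase; give rasburicase; if rasburicase, no bicarbonate. There are four possible actions:

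| Bicarbonate | Rasburicase | What is breached |
|---|---|---|
| Yes | Yes | Both caveats |
| Yes | No | Uric acid row's instruction |
| No | Yes | Potassium row's instruction |
| No | No | Both instructions |

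Every action breaches at least one statement.

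**Step 3. Find the situations where this arises.**

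| Situation | Forced conflict? |
|---|---|
| Potassium row met, uric acid below 8.0 mg/dL | No, unless rasburicase has already been given |
| Potassium row met, uric acid 8.0 to below 10 mg/dL without the qualifying rises | No, because rasburicase is only to be considered, unless it has already been given |
| Potassium row met, higher uric acid row met at the same time | Yes |
| One of these two rows followed first, the other met later | Yes, since no time limit is put on either caveat |
| Rasburicase given as prophylaxis, potassium row met later | Only if the caveat, printed under hyperuricemia treatment, is read as covering prophylaxis |

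Both triggers are wider than the single cut-offs of 6.0 mmol/L and 10 mg/dL. The potassium row also applies to symptoms, and the uric acid row has its second limb. The creatinine rise of 0.3 mg/dL in that limb is also Appendix H's creatinine criterion for acute kidney injury, which counts as clinical TLS unless attributable to another cause.

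**Step 4. Look for a precedence rule.** None appears in the TLS text of Sections 5.1, 5.3.1.1 and 6.1.8.2, in Appendix E or in Appendix H. Nothing says which row governs, how long an exclusion lasts after a dose, or what to do if the excluded drug has already been given.

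**Step 5. Check whether the wording could be conditional.** In the same potassium row, calcium gluconate is tied to ECG or telemetry evidence of life-threatening arrhythmia. The lower uric acid row uses the verb consider. The table uses conditional wording elsewhere; the two instructions at issue have none.

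**The case against.** Appendix E is titled as recommendations, and its caveats are advisory in tone. The if-clauses can be read as meaning that whichever drug is given first rules out the other. On that reading the table does its main job, because every row that names either drug as treatment warns against combining them. This stands in part: the combination is flagged throughout. But the text does not say that the first drug settles the matter. That reading also leaves the choice open when both triggers appear in the same set of results, and the second row's instruction remains unqualified when they appear in sequence.

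A reader might infer that any laboratory TLS with potassium above 6 mmol/L and uric acid above 8 mg/dL forces the conflict. The documents do not support this. Between 8.0 and 10 mg/dL without the qualifying rises, a site may decline rasburicase and comply with both rows.

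A reader might also infer that the table as a whole cannot be followed. It can, apart from the two drug instructions and their caveats: rechecks, nephrology contact and the other measures in both rows do not conflict.

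The prophylaxis case is weaker. The specific clause in Section 6.1.8.2 covers allopurinol-allergic subjects under the Version 1 and Amendment 1 heading, and extending a treatment caveat to an earlier prophylactic dose is an inference.

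On practical weight, Section 6.1.8.2 reports no clinical TLS in 94 subjects across AML studies. Section 5.6.4 says that potassium and phosphate changes in the monotherapy study were managed with Appendix E. The efficacy SAP, Section 5.0, records enrolment as complete, so most ramp-up exposure should be over. All of this stands and limits the importance of the point. It does not remove the contradiction: Section 6.1.8.2 still calls for TLS monitoring during continued dosing, and Section 5.1 allows treatment to be resumed after some discontinuations.

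**Conclusion.** The contradiction is real but narrow. It arises when the top potassium row and the higher uric acid row of Appendix E both apply, at once or one after the other, and it is confined to one drug instruction and its caveat in each row. The simultaneous case needs only the text as printed. The sequential case also takes the caveats as having no time limit, since none is stated. The prophylaxis case is secondary, because it also requires the caveat to reach beyond the treatment row where it is printed.

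How often the pair occurs is not given and cannot be derived from the documents. The absence of clinical TLS in 94 subjects does not bound how often the two laboratory triggers coincide. No endpoint, sample size or analysis is affected. The point is worth correcting because it bears on subject safety and the correction is small. This review takes no position on which instruction should prevail.

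**What to change.** The sponsor's medical team should reconcile the two Appendix E rows with each other and with Section 6.1.8.2. The text should be possible to follow when both triggers are met and when one of the two drugs has already been given, and it should say whether prophylactic rasburicase counts for this purpose. The clinical content of that rule is for the medical team.

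The cost is a short clarification in Appendix E and a site memo, with no added procedures, data collection or analysis. With enrolment complete, few subjects in this study are likely to benefit.

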Appendix G. Cell Lines Table

Venetoclax is potent against AML cell lines treated in vitro. AML cell lines were treated with increasing concentrations of venetoclax for 48 hours before assessing cell viability. Venetoclax cell killing IC50 values are shown for each cell line.

Cell Line	Venetoclax IC50 (µM)	Genetic Lesions
MOLM-13	< 0.100	MLL- and FLT3-mutant
GDM-1	< 0.100	nd
EOL-1	< 0.100	MLL-mutant
HL-60	< 0.100	N-Ras-mutant
MV4-11	< 0.100	MLL- and FLT3-mutant
ML-2	< 0.100	MLL-mutant
SIG-M5	< 0.100	nd
OCI-AML2	< 0.100	nd
MOLM-16	0.040	nd
OCI-AML5	0.110	nd
THP-1	0.820	MLL- and N-Ras-mutant
Kasumi-1	1.000	t(8;21) translocation
KG-1	1.200	nd
HNT-34	1.700	nd
PL-21	1.810	FLT3-mutant
SKM-1	2.530	nd
UKE-1	3.060	JAK2-mutant
SET-2	3.330	JAK2-mutant
HEL	3.370	JAK2-mutant
OCI-M2	4.050	nd
OCI-AML3	5.450	N-Ras-mutant
OCI-M1	5.610	nd
NOMO-1	6.950	MLL-mutant
ME-1	> 10	N-Ras-mutant and inv16

nd = not determined

Appendix H. Tumor Lysis Syndrome Classification

Metabolic Abnormality	Criteria for Classification of Laboratory Tumor Lysis Syndrome*	Criteria for Classification of Clinical Tumor Lysis Syndrome**
Hyperuricemia	Uric acid > 8 mg/dl (475.8 µmol/liter)	N/A
Hyperphosphatemia	Phosphorus > 4.5 mg/dl (1.5 mmol/liter)	N/A
Hyperkalemia	Potassium > 6 mmol/liter	Cardiac dysrhythmia or sudden death probably or definitely caused by hyperkalemia
Hypocalcemia	Corrected calcium < 7.0 mg/dl (1.75 mmol/liter) or ionized calcium < 1.12 mg/dl (0.3 mmol/liter) [#]	Cardiac dysrhythmia, sudden death, seizure, neuromuscular irritability (tetany, paresthesias, muscle twitching, carpopedal spasm, Trousseau's sign, Chvostek's sign, laryngospasm, or bronchospasm), hypotension, or heart failure probably or definitely caused by hypocalcemia
Acute Kidney Injury [!]	N/A	Increase in the serum creatinine level of 0.3 mg/dl (26.5 µmol/liter) or the presence of oliguria (average urine output of < 0.5 ml/kg/hr over a 6-hour period)

* Laboratory TLS requires two or more metabolic abnormalities must be present during the same 24-hour period within 3 days before the start of therapy or up to 7 days afterward.

** Clinical TLS requires the presence of Laboratory TLS plus one or more findings from the Clinical TLS column.

Corrected calcium = measured calcium level in mg/dl + 0.8 × (4 – albumin in gm/dl).

! Acute kidney injury, unless attributable to another cause, represents clinical TLS even if criteria for laboratory TLS are not satisfied.

Cross reference: Howard SC 2011⁴³

Appendix I. Protocol Amendment: List of Changes

A summary of changes is listed in Section 1.1.

Specific Protocol Changes

Section 1.3 List of Abbreviations and Definition of Terms

Subsection Abbreviations

Add:

COVID-19	Coronavirus Disease-2019
DTP	Direct-to-patient

Section 3.3 Benefits and Risks

Add: new last paragraph

Considering the coronavirus (COVID-19) pandemic, the benefit and risk to subjects participating in this study has been re-evaluated. Subjects receiving venetoclax may be at an increased risk for COVID-19 infection or experience serious illness if infected. Management of these adverse events will be made on a case-by-case basis with consideration of benefit/risk. However, based on the population and disease being studied and the anticipation that COVID-19 related risks are not expected to differ substantially between study subjects and the broader population of subjects receiving treatment for AML, no change to the benefit/risk balance for subjects in this study is expected.

**Table 3. Study Activities (Phases 1 and 2 {Including Cohort C})
Previously read:**

Procedures	Scr ^a	Day -1	Cycle 1					Day 1 of Cycle 2 and Day 1 of Every Cycle Thereafter (± 3 Days)	Cycle 2 Day 1, Cycle 4 Day 1, and Every 3 Cycles Thereafter (± 7 Days)	Final Visit ⁿ	30-Day Safety F/U	PT F/U ^u (± 1 Week)
			Day 1	Day 2	Day 3	Day 4	Day 5					
Informed Consent	X ^b											
Medical/Oncology History Assessment	X		X ^c									
Cytogenetic Assessment ^d	X											
AE/Concomitant Medication Assessment	X	X	X	X	X	X	X	X		X	X	
Tumor Lysis Syndrome Prophylaxis ^e		X	X	X	X	X	X					
Physical Exam (including weight) ^f	X ^h		X				X ⁱ	X ^j		X ^j	X ^j	
Vital Signs ^f	X	X	X	X	X	X	X	X		X	X	
ECOG Performance Status ^f	X		X					X		X	X	
Hematology ^{f,g}	X		X	X	X	X	X	X		X	X	X
Chemistry ^{e,f}	X ^k		X	X	X	X	X	X ^k		X ^k	X	
Coagulation ^f	X		X					X ^l		X	X	
Urinalysis ^f	X											
12-lead ECG ^m	X									X ^o		
MUGA (preferred)/2D Echocardiogram w/Doppler ^{m,p}	X											
Clinical Disease Progression Assessment									X	X		X

Procedures	Scr ^a	Day -1	Cycle 1					Day 1 of Cycle 2 and Day 1 of Every Cycle Thereafter (± 3 Days)	Cycle 2 Day 1, Cycle 4 Day 1, and Every 3 Cycles Thereafter (± 7 Days)	Final Visit ⁿ	30-Day Safety F/U	PT F/U ^u (± 1 Week)
			Day 1	Day 2	Day 3	Day 4	Day 5					
Bone Marrow Aspirate and Biopsy for Response Assessment	X ^q							X ^r	X			
Dispense Subject Calendar/Diary							X ^s	X				
Collect Study Drug and Subject Calendar/Diary								X	X			
Survival Assessments ^t											X	

Scr = Screening; F/U = Follow-Up; PT = Post-Treatment

- a. Screening procedures must be performed within 21 days prior to initial study drug administration.
- b. Obtain informed consent prior to performing any screening or study-specific procedures.
- c. On Cycle 1 Day 1, any additional medical history that is observed after signing of the informed consent but prior to initial study drug administration and not considered related to study-required procedures will be recorded in the subject's medical history.
- d. Cytogenetic testing should be performed if not completed within 3 months prior to Screening.
- e. All subjects must receive tumor lysis prophylaxis prior to and during treatment. For details on tumor lysis prophylaxis and management, refer to Section 6.1.8.2 Management of Tumor Lysis Syndrome (TLS) and Appendix E– Recommendations for Initial Management of Electrolyte Imbalances and Prevention of Tumor Lysis Syndrome (TLS) for further information.
- f. For all study visits beginning with Cycle 3, physical examination, vital signs, ECOG performance status, hematology, chemistry, coagulation and urinalysis may be performed within 72 hours before Day 1 of treatment for that cycle.
- g. Hematology will be performed weekly (at the minimum, hematology should be performed weekly during Cycle 1 and Cycle 2).
- h. Height will be measured only at Screening.
- i. Only applies to Dose Level (-)2. Subjects should have Physical exam upon discharge from the hospital. Subjects should remain hospitalized no less than 24 hours post dosing of their designated cohort dose. Also, Dose Levels 4 and 5 would stay in hospital until Day 8, needing a Physical exam at Day 8.
- j. A symptom-directed physical exam may be performed.
- k. Amylase and lipase are required at Screening, Cycle 2 Day 1, and the Final Visit.
- l. Coagulation to be performed on Cycle 2 Day 1 and not required subsequently unless clinically indicated.

- m. Additional ECGs and a MUGAs/Echos should be performed as clinically necessary per the discretion of the investigator.
- n. Final Visit procedures should be performed when a subject discontinues from the study.
- o. May be obtained \pm 2 days of the visit.
- p. Should be performed provided that such assessment would not inappropriately delay therapy per discretion of the investigator.
- q. Historical bone marrow aspirates at screening will not be sufficient; a bone marrow aspirate must be performed for study entry to collect mandatory biomarker assessments.
- r. May be performed \pm 7 days of the anticipated Day 1 of the subsequent cycle visit, for visits beginning with Cycle 2 Day 1. Assessments beginning with Cycle 4 Day 1 should be performed and resulted prior to the dispensation of the next cycle of drug.
- s. Diaries will be dispensed upon discharge from the hospital.
- t. Survival assessments should be performed every 12 weeks (\pm 1 week) for 1 year after last subject's last dose.
- u. Post Treatment visits will be performed every 12 weeks (\pm 1 week) for up to 1 year after last subject's last dose. Survival assessments will be performed every 12 weeks, beginning when subjects develop progressive disease, for 1 year after the last subject's last dose.

Note: Refer to Table 4 for treatment schedule.

Has been changed to read:

Procedures	Scr ^a	Day -1	Cycle 1					Day 1 of Cycle 2 and Day 1 of Every Cycle Thereafter (\pm 3 Days)	Cycle 2 Day 1, Cycle 4 Day 1, and Every 3 Cycles Thereafter (\pm 7 Days)	Final Visit ⁿ	30-Day Safety F/U	PT F/U ^u (\pm 1 Week)
			Day 1	Day 2	Day 3	Day 4	Day 5					
Informed Consent	X ^b											
Medical/Oncology History Assessment	X		X ^c									
Cytogenetic Assessment ^d	X											
AE/Concomitant Medication Assessment ^v	X	X	X	X	X	X	X	X		X	X	
Tumor Lysis Syndrome Prophylaxis ^e		X	X	X	X	X	X					
Physical Exam (including weight) ^{f,v}	X ^h		X				X ⁱ	X ^j		X ^j	X ^j	

Procedures	Scr ^a	Day -1	Cycle 1					Day 1 of Cycle 2 and Day 1 of Every Cycle Thereafter (± 3 Days)	Cycle 2 Day 1, Cycle 4 Day 1, and Every 3 Cycles Thereafter (± 7 Days)	Final Visit ⁿ	30-Day Safety F/U	PT F/U ^u (± 1 Week)
			Day 1	Day 2	Day 3	Day 4	Day 5					
Vital Signs ^{f,v}	X	X	X	X	X	X	X	X		X	X	
ECOG Performance Status ^{f,v}	X		X					X		X	X	
Hematology ^{f,g,v}	X		X	X	X	X	X	X		X	X	X
Chemistry ^{e,f,v}	X ^k		X	X	X	X	X	X ^k		X ^k	X	
Coagulation ^{f,v}	X		X					X ^l		X	X	
Urinalysis ^{f,v}	X											
12-lead ECG ^{m,v}	X									X ^o		
MUGA (preferred)/2D Echocardiogram w/Doppler ^{m,p}	X											
Clinical Disease Progression Assessment									X	X		X
Bone Marrow Aspirate and Biopsy for Response Assessment	X ^q								X ^r	X		
Dispense Subject Calendar/Diary							X ^s	X				
Collect Study Drug and Subject Calendar/Diary ^w								X		X		
Survival Assessments ^t												X

Scr = Screening; F/U = Follow-Up; PT = Post-Treatment

- Screening procedures must be performed within 21 days prior to initial study drug administration.
- Obtain informed consent prior to performing any screening or study-specific procedures.
- On Cycle 1 Day 1, any additional medical history that is observed after signing of the informed consent but prior to initial study drug administration and not considered related to study-required procedures will be recorded in the subject's medical history.
- Cytogenetic testing should be performed if not completed within 3 months prior to Screening.

- e. All subjects must receive tumor lysis prophylaxis prior to and during treatment. For details on tumor lysis prophylaxis and management, refer to Section 6.1.8.2 Management of Tumor Lysis Syndrome (TLS) and [Appendix E](#) – Recommendations for Initial Management of Electrolyte Imbalances and Prevention of Tumor Lysis Syndrome (TLS) for further information.
- f. For all study visits beginning with Cycle 3, physical examination, vital signs, ECOG performance status, hematology, chemistry, coagulation and urinalysis may be performed within 72 hours before Day 1 of treatment for that cycle.
- g. Hematology will be performed weekly (at the minimum, hematology should be performed weekly during Cycle 1 and Cycle 2).
- h. Height will be measured only at Screening.
- i. Only applies to Dose Level (-)2. Subjects should have Physical exam upon discharge from the hospital. Subjects should remain hospitalized no less than 24 hours post dosing of their designated cohort dose. Also, Dose Levels 4 and 5 would stay in hospital until Day 8, needing a Physical exam at Day 8.
- j. A symptom-directed physical exam may be performed.
- k. Amylase and lipase are required at Screening, Cycle 2 Day 1, and the Final Visit.
- l. Coagulation to be performed on Cycle 2 Day 1 and not required subsequently unless clinically indicated.
- m. Additional ECGs and a MUGAs/Echos should be performed as clinically necessary per the discretion of the investigator.
- n. Final Visit procedures should be performed when a subject discontinues from the study.
- o. May be obtained \pm 2 days of the visit.
- p. Should be performed provided that such assessment would not inappropriately delay therapy per discretion of the investigator.
- q. Historical bone marrow aspirates at screening will not be sufficient; a bone marrow aspirate must be performed for study entry to collect mandatory biomarker assessments.
- r. May be performed \pm 7 days of the anticipated Day 1 of the subsequent cycle visit, for visits beginning with Cycle 2 Day 1. Assessments beginning with Cycle 4 Day 1 should be performed and resulted prior to the dispensation of the next cycle of drug.
- s. Diaries will be dispensed upon discharge from the hospital.
- t. Survival assessments should be performed every 12 weeks (\pm 1 week) for 1 year after last subject's last dose or possibly sooner if all patients have discontinued and most patients have expired.
- u. Post Treatment visits will be performed every 12 weeks (\pm 1 week) for up to 1 year after last subject's last dose or possibly sooner if all patients have discontinued and most patients have expired. Survival assessments will be performed every 12 weeks, beginning when subjects develop progressive disease, for 1 year after the last subject's last dose or possibly sooner if all patients have discontinued and most patients have expired.
- v. Procedure may be performed in the subject's home or local hospital/clinic by adequately trained personnel if required due to COVID-19 restrictions.
- w. Venetoclax may be shipped directly to a subject's home only if required due to COVID-19 restrictions.

Note: Refer to [Table 4](#) for treatment schedule.

Section 5.3.1.1 Study Procedures

Add: new second paragraph

Study visits may be impacted due to the COVID-19 pandemic. This may include changes such as phone or virtual visits, visits at alternative locations, or changes in the visit frequency and timing of study procedures, among others. Additional details are provided in the subsequent section. Every effort should be made to ensure the safety of subjects and site staff, while maintaining the integrity of the study. If visits cannot be conducted onsite due to travel restrictions or other pandemic-related reasons, follow [Table 3](#) on how to proceed.

Section 5.3.1.1 Study Procedures

Subsection Vital Signs

Heading "COVID-19 Pandemic-Related Acceptable Protocol Modifications"

Add: new heading title and text

COVID-19 Pandemic-Related Acceptable Protocol Modifications

Due to the COVID-19 pandemic, subject visits may be conducted via phone or video conference. In these situations, weight, blood pressure, vitals and respiratory rate measurements may be performed by the subject or caregiver as needed.

Section 5.3.1.1 Study Procedures

Subsection 12-Lead Electrocardiogram (ECG)

Heading "COVID-19 Pandemic-Related Acceptable Protocol Modifications"

Add: new heading title and text

COVID-19 Pandemic-Related Acceptable Protocol Modifications

In the event this may not be performed due to study modifications related to the COVID-19 pandemic, perform the 12-lead ECG at the next earliest feasible visit or arrange to have an alternative acceptable local facility perform the ECG for the subject.

Section 5.3.1.1 Study Procedures

Subsection Clinical Laboratory Tests

Heading "COVID-19 Pandemic-Related Acceptable Protocol Modifications"

Add: new heading title and text

COVID-19 Pandemic-Related Acceptable Protocol Modifications

If travel restrictions or other changes in local regulations in light of the COVID-19 pandemic prevent the subject from having blood drawn for laboratory testing at the study site, if possible, arrange for subjects to have laboratory work done at a local lab, hospital, or other facility. Local lab results should be obtained along with reference ranges and kept within the subjects' source documentation. Local lab results should be reviewed by the investigator as soon as possible.

If laboratory samples cannot be obtained, study drug administration may be continued provided the investigator has reviewed all prior laboratory results and confirms and discusses with the subject that there is no safety concern for the subject to continue use of the study drug in the absence of current labs. The subject should be scheduled for laboratory draws as soon as feasible from the scheduled visit.

Section 5.3.1.1 Study Procedures

Subsection Post-Treatment Follow-Up Visit(s)

First sentence previously read:

For subjects who discontinue study treatment for reasons other than disease progression, the following post-treatment assessments will be performed every 12 weeks (\pm 1 week) until criteria are met for discontinuation from the study (e.g., disease progression, death or a subject's refusal of the Post-Treatment visits) for a period of 1 year after last subject's last dose:

Has been changed to read:

For subjects who discontinue study treatment for reasons other than disease progression, the following post-treatment assessments will be performed every 12 weeks (\pm 1 week) until criteria are met for discontinuation from the study (e.g., disease progression, death or

a subject's refusal of the Post-Treatment visits) for a period of 1 year after last subject's last dose or possibly sooner if all patients have discontinued and most patients have expired:

Section 5.3.1.1 Study Procedures
Subsection Survival Assessment(s)
Previously read:

Survival information (e.g., date and cause of death, post-treatment cancer therapies, including transplantation) will be collected once the subject's disease has progressed via telephone calls (e.g., to subject or family member) and/or clinical visits at 12 weeks intervals (± 1 week) after the subject's last study visit for a period of 1 year after last subject's last dose.

Has been changed to read:

Survival information (e.g., date and cause of death, post-treatment cancer therapies, including transplantation) will be collected once the subject's disease has progressed via telephone calls (e.g., to subject or family member) and/or clinical visits at 12 weeks intervals (± 1 week) after the subject's last study visit for a period of 1 year after last subject's last dose or possibly sooner if all patients have discontinued and most patients have expired.

Section 5.4.1 Discontinuation of Individual Subjects
Sixth paragraph previously read:

Post-treatment assessment will be performed every 12 weeks (± 1 week) until discontinuation from the study (e.g., disease progression death or a subject's refusal of the Post-Treatment visits) for a period of 1 year after last subject's last dose.

Has been changed to read:

Post-treatment assessment will be performed every 12 weeks (± 1 week) until discontinuation from the study (e.g., disease progression death or a subject's refusal of the

Post-Treatment visits) for a period of 1 year after last subject's last dose or possibly sooner if all patients have discontinued and most patients have expired.

Section 5.4.1 Discontinuation of Individual Subjects

Seventh paragraph previously read:

Survival information (e.g., date and cause of death, post-treatment cancer therapies, including transplantation) will be collected once the subject's disease has progressed via telephone calls (e.g., to subject or family member) and/or clinical visits at 12 weeks intervals (± 1 week) after the subject's last study visit for a period of 1 year after last subject's last dose.

Has been changed to read:

